## 7.2 Study Conduct

### 7.2.1 Accrual

The accrual pattern will be summarized per country, investigational site, and per month for all randomized subjects. Randomization date (if applicable), first dosing date, country, investigational site will be presented in a by subject listing of accrual.

Furthermore, the accrual pattern will be summarized by the stratification factors PD-L1 status and M Stage.

### 7.2.2 Relevant Protocol Deviations

The following programmable deviations will be considered as relevant protocol deviations and summarized by treatment group and overall. Non-programmable relevant eligibility and on treatment protocol deviations, as well as significant (both programmable and non programmable) eligibility and on-treatment protocol deviations will be reported through ClinSIGHT listings.

At Entrance:

- Subjects with baseline ECOG performance status > 1
- Subjects who received prior systemic anti-cancer treatment in the metastatic setting
- Subjects without histologically documented Stage III or Stage IV melanoma, as per AJCC staging system

On-study:

- Subjects receiving anti-cancer therapy (chemotherapy, hormonal therapy, immunotherapy, standard or investigational agents for treatment of cancer) while on study therapy
- Subjects treated differently than as randomized (subjects who received the wrong treatment, excluding the never treated)

Listings will also be provided.

### **7.3 Study Population**

Summaries of study population will be based on all treated subjects, except that of subject disposition which will be based on all enrolled subjects.

#### **7.3.1 Subject Disposition**

The total number of subjects enrolled (randomized or not randomized) will be presented along with the reason for not being randomized. This analysis will be performed on the all enrolled population only.

Number of subjects who discontinued study treatment during Part 1 and during the overall study for All Treated Subjects and during Part 2 for All Subjects Treated in Part 2, along with corresponding reason for discontinuation will be tabulated by treatment group as treated. Reason for discontinuation will be derived from subject status CRF page.

Number of subjects randomized but not treated along with the reason will be tabulated by treatment group as randomized. This analysis will be performed on the all randomized population only.

A subject listing for all randomized subjects will be provided showing the subject's randomization date (if applicable), first and last dosing date, off study date and reason for going off-study. A subject listing for subjects not randomized will also be provided, showing the subject's race, gender, age, consent date and reason for not being randomized.

#### **7.3.2 Demographics and Baseline Characteristics**

The following baseline characteristics will be summarized by treatment group, for the population of All Treated Subjects. All baseline presentations will identify subjects with missing measurements. Listings will also be provided.

- Age (descriptive statistics)
- Age category I (< 65, ≥ 65- < 75, ≥ 75)
- Age category II (< 65, ≥ 65)
- Gender (male, female)
- Race (white, black, asian, other)
- Region (EU, Australia)
- Baseline ECOG Performance Status (0, 1)
- M Stage at Study Entry (M0, M1a, M1b, M1c) (source: CRF)
- AJCC Stage at Study Entry (III, IV)
- Weight (descriptive statistics)
- PD-L1 Status (≥5%, <5%/indeterminate) (source: clinical database)
- BRAF mutation status (BRAF mutant, wildtype) (source: CRF)

- BRAF mutation test (Cobas+THxID, Other, Unknown)
  - Baseline LDH ( $\leq$  ULN,  $>$  ULN)
  - Baseline LDH ( $\leq 2*ULN$ ,  $> 2*ULN$ )
  - History of Brain Metastases (Yes, No)
  - Smoking Status (Yes, No)
  - Time from Initial Disease Diagnosis to Randomization ( $< 1$  year,  $1-< 2$  year,  $2-< 3$  year,  $3-< 4$  year,  $4-< 5$  year,  $\geq 5$  year)
  - All lesions (Investigator Tumor Assessments at Baseline): sites of disease, number of disease sites per subject.
  - Target lesions (Investigator Tumor Assessments at Baseline): Presence of target lesions, site of target lesion, sum of longest diameter of target lesion.
- Similarly the following IVRS data will be summarized by treatment group as randomized.
- M Stage at Study Entry (M0/M1a/M1b/M1c)
  - PD-L1 Expression Level ( $\geq 5\%$  and  $< 5\%$ /indeterminate)

### **7.3.3 Medical History**

General medical history will be listed by subject.

### **7.3.4 Prior Therapy**

The following will be summarized by treatment group for All Treated Subjects.

- Prior neo-adjuvant therapy (yes/no)
- Prior adjuvant therapy (yes/no)
- Time from completion of prior adjuvant therapy to randomization ( $< 6$  months and  $\geq 6$  months) for subjects who received prior adjuvant therapy
- Prior surgery related to cancer (yes/no)
- Prior radiotherapy (yes/no)

Agents and medication will be reported using the generic name. A listing by subject will also be provided.

### **7.3.5 Baseline Examinations**

Subjects with abnormal baseline physical exam results will be tabulated by examination criteria (eg, neck, cardiovascular, lungs, etc) and by treatment group for All Treated Subjects.

### **7.3.6 Discrepancies between IVRS and CRF information**

Summary tables (cross-tabulations) of stratification factors for All Treated Subjects by treatment group will be provided to show any discrepancies between what was reported through IVRS vs. CRF data or clinical database (baseline).

- M Stage at Study Entry (IVRS vs. CRF data)
- PD-L1 status (IVRS vs. clinical database)

### **7.4 Extent of Exposure**

Analyses will be performed by treatment group “as treated” in all treated subjects, unless otherwise specified.

#### **7.4.1 Administration of Study Therapy**

The following parameters will be summarized (descriptive statistics) by treatment group:

- Time from randomization to first dose of study therapy (0 to 3 days, > 3 to 7, > 7 to 14, > 14 to 21, > 21 to 28, > 28)
- Number of concomitant doses received (nivolumab + ipilimumab).
  - For Arm B a subject will be considered to have received concomitant doses of nivolumab and ipilimumab if both infusions are administered on the same date.
  - For Arm A a subject will be considered to have received concomitant doses of nivolumab and ipilimumab if any FRC infusion was administered.

The following parameters will be summarized (descriptive statistics) by treatment group and study therapy (nivolumab and ipilimumab for Arm B, BMS-986214 for Arm A).during Part 1 for All Treated Subjects:

- Number of doses received
- Cumulative dose in mg/kg
- Relative dose intensity (%) using the following categories: < 50%; 50 - < 70%; 70 - < 90%; 90 - < 110%; ≥ 110%
- Infusion duration in minutes

In addition, the following parameters will be summarized (descriptive statistics) for nivolumab flat dosing during Part 2 for All Subjects Treated in Part 2:

- Number of doses received
- Cumulative dose in mg
- Relative dose intensity (%) using the following categories: < 50%; 50 - < 70%; 70 - < 90%; 90 - < 110%; ≥ 110%.
- Infusion duration in minutes.

Duration of treatment will be presented by treatment group using a Kaplan-Meier curve whereby the last dose date will be the event date for those subjects who are off study therapy. Median duration of treatment and associated 95% CI will be provided. Subjects who are still on study therapy will be censored on their last dose date. Duration of study therapy will also be summarized in a table with descriptive statistics (mean, minimum, and maximum). The percentage of subjects with study therapy duration > 3 months, > 6 months, > 9 months, and > 12 months will be tabulated.

A by-subject listing of dosing of study medication (record of study medication, infusion details, and dose changes) and a listing of batch numbers will be also provided.

**Table 7.4.1-1: Study Therapy Parameter Definitions During Part 1 (Combination Portion)**

	BMS-986214 (Co-administration FRC)	Nivolumab (Arm B)	Ipilimumab (Arm B)
Dosing Schedule per Protocol	4 mg/kg every 3 weeks for 4 doses	1 mg/kg every 3 weeks for 4 doses	3 mg/kg every 3 weeks for 4 doses
Dose	Dose (mg/kg) is defined as Total Dose administered (mg)/Most recent weight (kg). Dose administered in mg at each dosing date and weight are collected on the CRF.	Dose (mg/kg) is defined as Total Dose administered (mg)/Most recent weight (kg). Dose administered in mg at each dosing date and weight are collected on the CRF.	Dose (mg/kg) is defined as Total Dose administered (mg)/Most recent weight (kg). Dose administered in mg at each dosing date and weight are collected on the CRF.
Cumulative Dose	Cum Dose (mg/kg) is the sum of the doses administered to a subject during Part 1.	Cum Dose (mg/kg) is the sum of the doses administered to a subject during Part 1.	Cum Dose (mg/kg) is the sum of the doses administered to a subject during Part 1.
Relative Dose Intensity (%)	$\text{Cum dose} / [4 \times (\text{Last Part 1 dose date} - \text{Start dose date} + 21) / 21] \times 100$	$\text{Cum dose} / [1 \times (\text{Last Part 1 dose date} - \text{Start dose date} + 21) / 21] \times 100$	$\text{Cum dose} / [3 \times (\text{Last Part 1 dose date} - \text{Start dose date} + 21) / 21] \times 100$
Infusion Duration (mins)	Each infusion duration is calculated as infusion stop date/time - infusion start date/time.	Each infusion duration is calculated as infusion stop date/time - infusion start date/time.	Each infusion duration is calculated as infusion stop date/time - infusion start date/time.
Duration of Treatment	Last Part 1 dose date - Start dose date + 1	Last Part 1 dose date - Start dose date + 1	Last Part 1 dose date - Start dose date + 1

**Table 7.4.1-2: Study Therapy Parameter Definitions During Part 2 (Maintenance)**

	Nivolumab (Arms A and B)
Dosing Schedule per Protocol	480 mg flat dose every 4 weeks
Dose	Dose (mg) = total dose delivered as recorded on Record of Study Medication CRF
Cumulative Dose	Cum Dose (mg) is the sum of the doses administered to a subject during Part 2.
Relative Dose Intensity (%)	$[\text{Cumulative dose (mg)} / ((\text{Last dose date in Part 2} - \text{first dose date in Part 2} + 28) \times 480 / 28)] \times 100$

**Table 7.4.1-2: Study Therapy Parameter Definitions During Part 2 (Maintenance)**

Nivolumab (Arms A and B)	
Infusion Duration (mins)	Each infusion duration is calculated as infusion stop date/time - infusion start date/time.
Duration of Treatment	last dose date in Part 2- first dose date in Part 2 + 1

## **7.4.2 Modifications of Study Therapy**

### **7.4.2.1 Dose Delays**

Each nivolumab, ipilimumab, or BMS-986214 infusion may be delayed. A dose will be considered as actually delayed if the delay is exceeding 3 days (ie greater than or equal to 4 days from scheduled dosing date). All studies drugs must be delayed until treatment can resume. Reason for dose delay will be retrieved from CRF dosing pages.

The following parameters will be summarized by treatment group:

- Number of dose delays per subject, length of delay, and reason for delay

### **7.4.2.2 Infusion interruptions and Rate Changes**

Each nivolumab, ipilimumab, or BMS-986214 infusion can be interrupted and/or the IV infusion rate can be reduced. This information will be retrieved from CRF dosing pages.

The following parameters will be summarized by treatment group:

- Number of subjects with at least one dose infusion interruption, the reason for interruption, and the number of infusion interruptions per subject.
- Number of subjects with at least one IV infusion rate reduction and the reason for reduction.

### **7.4.2.3 Dose Escalations**

Dose escalations are not permitted for any study drug.

### **7.4.2.4 Dose Reductions**

Dose reductions are not permitted for any study drug.

### **7.4.2.5 Dose Omissions**

Dose omissions are not permitted for any study drug.

[REDACTED]

## 7.5 Efficacy

The primary endpoint is related to safety and there are no primary efficacy endpoints. Analysis methods for the primary safety endpoint are described in Section 7.6.1. Descriptive analyses of secondary and exploratory efficacy endpoints will be performed and are described below.

### 7.5.1 Objective Response Rate

ORRs (based on investigator assessments using RECIST 1.1 criteria) and corresponding 95% exact CIs will be calculated using the Clopper Pearson method for each of the treatment arms. BOR will be tabulated for each treatment group. Associated odds ratios and 95% CIs for Arm A relative to Arm B will be calculated using Cochran-Mantel-Haenszel (CMH) methodology, adjusting for the stratification factors PD-L1 expression and M stage at screening (IVRS source). An estimate of the difference in ORRs and corresponding 2-sided 95% CI will be calculated using CMH methodology, adjusting for the same stratification factors as above.

#### Subgroup Analysis

To assess consistency of treatment effects in ORR in different subsets, a “forest” plot of the unweighted differences in ORRs and corresponding exact 95% CIs using the Newcombe method will be produced for the following variables:

- PD-L1 Status ( $\geq 5\%$  expression and  $< 5\%$  expression/indeterminate) (source: clinical database)
- BRAF mutation status (BRAF mutant and wildtype)
- M Stage at Study Entry (M0/M1a/M1b and M1c) (source: CRF)
- Age category I ( $< 65$ ,  $\geq 65$ -  $< 75$ , and  $\geq 75$ )
- Age category II ( $< 65$  and  $\geq 65$ )
- Gender (male and female)
- Race (white, black, asian, and other)
- Region (EU, Australia)
- Baseline ECOG Performance Status (0 and 1)
- History of Brain Metastases (Yes and No)
- Baseline LDH ( $\geq$  ULN and  $>$  ULN)
- Baseline LDH ( $\leq 2$ \*ULN and  $>$  2\*ULN)
- AJCC Stage (III and IV)

If a subgroup category has less than 10 subjects per treatment group, ORR will not be computed/displayed.

For purposes of analysis, countries will be included in each region category according to [Table 7.5.1-1](#).

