## 7 STATISTICAL ANALYSES

### 7.1 General Methods

Unless otherwise noted, the following subsections describe tabulations of discrete variables, by the frequency and proportion of subjects falling into each category, grouped by treatment (with total). Percentages given in these tables will be rounded and, therefore, may not always sum to 100%. Continuous variables will be summarized by treatment group (with total) using the mean, standard deviation, median, minimum and maximum values. If a missing category is not being presented in the data display, only those subjects with non-missing values for the parameter being assessed are included in the percentage calculation.

Time to event distribution will be estimated using Kaplan Meier techniques. This will be done for endpoints progression free survival, overall survival and duration of response (note that TTR will be analyzed using summary statistics such as mean, SD, median, min, max). Median survival time along with 95% CI will be constructed based on a log-log transformed CI for the survivor function  $S(t)$ . Rates at fixed time points will be derived from the Kaplan Meier estimate and corresponding confidence interval will be derived based on Greenwood formula for variance derivation and on log-log transformation applied on the survivor function  $S(t)$ .

Confidence intervals for binomial proportions will be derived using the Clopper-Pearson method.

Formal hypothesis testing with control of Type I error will not be conducted for any of the endpoints in this study. No p-values will be presented. Confidence intervals, when presented, will be for descriptive purposes only and will not be adjusted for multiplicity.

Unless otherwise noted, safety analyses will be performed using the on-treatment definition for the entire study treatment period (i.e. combined Part 1 and Part 2 treatment periods) as defined in Section 6.1.2. Alternate analysis periods will be used for specific endpoints or selected analyses as described in the corresponding endpoint or analysis section of this SAP.

Please see the following sections for additional details:

- Section 4.1: Primary Endpoint: MedDRA Anaphylactic Reaction Broad Scope SMQ AE Incidence Rate
- Section 4.2.1: MedDRA Anaphylactic Reaction Narrow Scope SMQ AE Incidence Rate

- Section 4.2.2: Hypersensitivity/Infusion Reaction Select AE Incidence Rate
- Section 4.2.6: Objective Response Rate

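### SAP 7.5.1 writes the first LDH subgroup pair of the ORR forest plot as ≥ ULN and > ULN, so its two rows overlap and omit LDH below the ULN (minor correction)

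*SAP*

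**What the plan says.** The Subgroup Analysis part of SAP 7.5.1 calls for a forest plot of unweighted ORR differences between the arms, with confidence intervals, for 13 listed variables. Its purpose is "To assess consistency of treatment effects in ORR in different subsets". Two of the 13 are baseline LDH:

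- First LDH split: "Baseline LDH ( $\geq$ ULN and $>$ ULN", that is, ≥ ULN and > ULN.
- Second LDH split, on the next line: "Baseline LDH ( $\leq 2$ \*ULN and $>$ 2\*ULN", that is, ≤ 2×ULN and > 2×ULN.

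SAP 7.3.2, the list of baseline characteristics, gives the first split differently: "Baseline LDH ( $\leq$ ULN, $>$ ULN", that is, ≤ ULN and > ULN.

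A display rule applies to every row of the plot: "If a subgroup category has less than 10 subjects per treatment group, ORR will not be computed/displayed". SAP 7.1 makes all confidence intervals descriptive and adds: "No p-values will be presented". Neither document gives a reason for a ≥ ULN category, and protocol 8.4.2.1 describes no LDH subgroup that would override the SAP.

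**The concern.** A subgroup pair should place each subject with a measured value in exactly one row. The first LDH pair does not. If it were programmed as written, the two rows would hold almost the same subjects and would agree for that reason alone, so they could say nothing about whether the ORR difference is similar in normal and elevated LDH. No row of the plot would isolate normal LDH, because the second LDH split combines normal values with elevations up to twice the ULN.

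The text is an analysis instruction, and SAP 9 sends the SAP's analyses into the study report unless otherwise noted. Left alone, it leads either to an uninformative pair of rows or to a programmer quietly departing from the SAP.

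**Working it through.** The plan states no figure to reproduce here; the check is one of set membership, followed by an illustrative count.

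**Inputs.** The categories in SAP 7.5.1 (both LDH splits), the categories in SAP 7.3.2, and the target of 100 treated subjects, 50 per arm (protocol 8.1).

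**Step 1: membership.** Let x be baseline LDH divided by the ULN. As written, the rows are x ≥ 1 and x > 1. Under SAP 7.3.2 they are x ≤ 1 and x > 1.

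| x | In ≥ ULN | In > ULN | Rows, as written | Rows, per SAP 7.3.2 |
|---|---|---|---|---|
| 0.5 | no | no | 0 | 1 |
| 0.99 | no | no | 0 | 1 |
| 1.0 | yes | no | 1 | 1 |
| 1.01 | yes | yes | 2 | 1 |
| 1.5 | yes | yes | 2 | 1 |
| 2.0 | yes | yes | 2 | 1 |
| 2.5 | yes | yes | 2 | 1 |

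As written, the > ULN row lies wholly inside the ≥ ULN row, and only subjects with x exactly 1 separate them. With the SAP 7.3.2 wording, every value tested falls in one row.

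**Step 2: what the second LDH split recovers.** A subject with x below 1 satisfies x ≤ 2 and so appears in the ≤ 2×ULN row. So does a subject with x = 1.5. That row therefore keeps the normal-LDH subjects in the display but does not separate them from mild elevations.

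**Step 3: illustrative counts.** Let e be the share of treated subjects with LDH above the ULN. The documents do not give e; 20% to 50% is assumed, and values exactly at the ULN are ignored. Subjects in both rows = 100 × e. Subjects in neither row = 100 × (1 − e).

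| e | In both rows | In neither row |
|---|---|---|
| 20% | 20 | 80 |
| 30% | 30 | 70 |
| 40% | 40 | 60 |
| 50% | 50 | 50 |

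At the low end, 20% of 50 is 10 subjects per arm, right at the display threshold. If an arm fell below 10, the > ULN row would be suppressed, and the ≥ ULN row with it unless subjects exactly at the ULN made up the number.

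**The case against.** The strongest case against is that this is a slip that the SAP itself resolves. SAP 7.3.2 has the right categories for the same variable, the next line of the same list has the correct form at 2×ULN, and the other numeric splits in the list do not overlap. A competent programmer would probably notice. The mock-ups sit in a Data Presentation Plan that is not available here (SAP 9), so whether the slip would reach an output is unknown. All of this stands and is why the point is minor. It does not make the instruction correct as written.

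A second objection is that the finding rests on one symbol in text extracted by machine from a PDF. A misread symbol cannot be fully excluded. It is unlikely, because ≤ came through correctly both in the next line and in SAP 7.3.2, but the PDF should be checked first.

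Two stronger readings are tempting and are not supported:

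- *The error defeats the purpose of the forest plot, or loses the normal-LDH subjects.* It affects one of 13 variables. The normal-LDH subjects remain in the overall ORR comparison, in the rows for the other variables and, pooled, in the ≤ 2×ULN row. What is lost is a row that isolates them.
- *The error reaches the stratification, because elevated LDH is part of the M1c definition in protocol Appendix 4.* Randomisation uses M stage as entered in the IRT (SAP 2.2), and the adjusted ORR analysis uses the IVRS strata (SAP 7.5.1). Neither draws on this subgroup bullet.

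**Conclusion.** The point holds as a minor error. Read literally, the first LDH pair in SAP 7.5.1 is neither exclusive nor exhaustive, and it contradicts SAP 7.3.2. Over the assumed range of 20% to 50% with elevated LDH, at least half of the 100 planned treated subjects would be missing from the pair and everyone else, apart from any exactly at the ULN, would be counted twice. Those counts illustrate the set logic; they do not measure an effect on any conclusion.

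The consequence is limited to two near-duplicate rows in a descriptive plot of the sixth secondary endpoint, with no hypothesis test attached. The primary safety endpoint, sample size, stratification, adjusted ORR estimate and baseline LDH table do not depend on it. The verdict assumes that the PDF shows the same symbol as the extracted text; if it shows ≤, there is nothing to correct.

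**What to change.** Confirm the symbol in the source PDF. If it is ≥, change the first LDH pair in SAP 7.5.1 to ≤ ULN and > ULN, matching SAP 7.3.2, and check that the forest-plot specification in the Data Presentation Plan uses the same categories. Do this before the final analysis, when SAP 4.2 schedules the efficacy endpoints. The cost is one symbol and a line in the SAP change record; no other analysis changes.

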**Table 7.5.1-1: Region Definition**

Country	Region
France	EU
Italy	EU
Spain	EU
Australia	Australia

#### Duration of Objective Response

DOR curves in each treatment group will be estimated using the KM product-limit method for subjects with a BOR of CR or PR. Median DOR, corresponding two-sided 95% CI, and range will be reported.

#### Time to Objective Response

Summary statistics of TTR will be provided by treatment group for subjects with a BOR of CR or PR. TTR curves will be estimated using the KM product-limit method in all treated subjects and will represent the cumulative rate of response over time. For non-responders, subjects will be censored at the maximum time of response + 1 day of all subjects in their respective treatment group. Cumulative response rates will be tabulated at Week 12 and Month 6.

#### Other Analyses

The following subject-level graphics will be provided by treatment group.

- For responders only, the time course of the following events of interest will be graphically displayed: tumor response, tumor progression, last dose received, and death.
- For response-evaluable subjects (treated subjects with baseline and at least one on-study tumor assessment), a waterfall plot showing the best reduction in target lesion tumor burden based on investigator assessment.

